For this safety and feasibility study, two clinical sites are being planned in the US (Eugene, Seattle) and one in China (Shanghai). An expert epileptologist will provide medical guidance at each site. The Chair of the Study Monitoring Committee will not be associated with these sites or with EGI: [name], Cincinnati Children's Hospital Medical Center. Racial and gender composition will be as it appears in each sample. Study protocols and safety procedures have been approved by IRBs in Eugene and Seattle, and are under review at Huashan Hospital in Shanghai.

Patient Recruitment

Adult and adolescent patients (12 and older, including males and females) are recruited who continue to have seizures after having achieved adequate dosage on each of two antiepileptic drugs. Patients are selected who have focal spikes (and other discharges of focal onset, including seizures) identified through Electrical Source Imaging (ESI) applied to a routine dense array EEG (dEEG) evaluation. All patients agree to maintain their current antiepileptic drug dose throughout the study, including the two month baseline and the two month follow-up period.

Inclusion Criteria

- (1) Partial onset seizures (simple or complex) with failure of adequate seizure control after prior use of at least 2 anti-seizure drugs at effective doses.
- (2) A clearly identified and localizable focus of epileptiform discharges, as defined by the discharges (typically epileptiform spikes) and as identified by dEEG assessment through one or more routine clinical dEEG evaluations.
- (3) Two or more partial seizures, with or without secondary generalization, in the last month, but less than 10 seizures per day.
- (4) Anti-seizure drug regimen has remained unchanged for the month before study entry, and there is reasonable likelihood of stability for the duration of the study, with the exception of allowing short-term rescue medications, such as lorazepam.
- (5) A history of epilepsy for at least 2 years. 33

Exclusionary Criteria

- (1) If of childbearing potential, the patient must agree to use an effective method of birth control during the study and cease participation if pregnant.
- (2) A history or condition of progressive brain disorders, serious systemic diseases, symptomatic cerebrovascular disease, cardiac disease, or alcohol abuse. Special conditions, for example, non-malignant brain tumors and vascular malformations, can be considered for entry on a case-by-case basis.

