- (3) A history or condition of status epilepticus or psychogenic seizures.

- (4) Presence of a cardiac pacemaker, vagus nerve stimulator, or metal implantation in the body (other than the teeth) including neurostimulators, cochlear implants, and implanted medication pumps.
- (5) Previous surgery involving opening the skull.
- (6) Allergy to or condition contraindicating lidocaine.
- (7) Unable to express presence of pain or discomfort.

Escape Criteria

For individual patients, the study will be terminated for any of the following reasons:

- (1) Unacceptable discomfort or pain at stimulation currents of 200 μ A.
- (2) A tonic-clonic seizure occurring during a stimulation session.
- (3) Emergence of a first-in-life tonic-clonic seizure at any time during the study.
- (4) Status epilepticus.
- (5) A two-fold increase of seizure frequency over the baseline seizure frequency. If the frequency of seizures is very low, then an apparent increase during treatment (not reliably quantified as a two-fold increase) will be discussed with the patient, family, physician and Study committee.

The entire study will terminate if 5 subjects meet escape criteria.

Baseline Evaluation

During a one-month pre-treatment baseline evaluation period, the patient (and/or family) will maintain the seizure diary, which will be reviewed by the study coordinator in a phone contact once per week. In addition, two two-hour routine dEEG evaluations will be conducted in the baseline evaluation period, including the opportunity for sleep for patients who may have interictal events in sleep or drowsiness. Each baseline evaluation also includes the California Verbal Learning Test, and the Quality of Life in Epilepsy report.

Probe Treatment and Evaluation

The GTEN Plan is developed to apply current pulses to the epileptic focus, as it is identified from the dEEG source localization of the spike onset. The GTEN Plan will often include more than one treatment option, primarily depending on the orientation of the cortical region identified as the epileptic focus. To evaluate a treatment targeting option, a probe treatment may be conducted, consisting of one 17-min pulsed treatment block (Figure 10) followed by one hour of dEEG evaluation and spike counting. If multiple targeting options are evaluated, the one with the best evidence of spike suppression will be selected for the 5 session treatment intervention.

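### As written, a first-in-life tonic-clonic seizure before any stimulation counts towards the five escapes that end the whole study, and a second stopping rule in the protocol conflicts with this

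*Protocol*

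**What the plan says.** Escape Criteria lists five reasons for ending an individual patient's participation and then adds a study-level rule: "The entire study will terminate if 5 subjects meet escape criteria". That rule gives no start of counting, no denominator and no requirement that the event be attributed to stimulation.

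The five criteria differ in their time windows:

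- Criterion 1: "Unacceptable discomfort or pain at stimulation currents of 200" μA. This is tied to stimulation.
- Criterion 2: "A tonic-clonic seizure occurring during a stimulation session". This is tied to a session.
- Criterion 3: "Emergence of a first-in-life tonic-clonic seizure at any time during the study". The window is the whole study.
- Criterion 4: "status epilepticus". No window is stated.
- Criterion 5: "A two-fold increase of seizure frequency over the baseline seizure frequency". This is measured against baseline.

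Patient Recruitment asks patients to hold their drug dose "throughout the study, including the two month baseline and the two month follow-up period", so it treats the baseline as part of the study. Baseline Evaluation gives a different length: "During a one-month pre-treatment baseline evaluation period".

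The Study Monitoring Committee section has its own rule. When more than five patients have worsened seizures and meet the same escape criteria, treatment is suspended at that site. Whether to end the trial at all sites is then for the Committee to decide.

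**The concern.** The stated goal of this open-label, uncontrolled study is to evaluate the safety, comfort and preliminary efficacy of stimulation. An event before any current has been delivered says nothing about the device. If such an event uses one of five places, the study could stop partly on natural history, and there is no control arm to show that this had happened. Patients enter with drug-refractory partial seizures, with or without secondary generalization, so a background tonic-clonic seizure during the untreated period is plausible. Each one that counts uses one fifth of the allowance.

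The protocol itself states both the rule and its window. This is therefore not a detail left to a later analysis plan.

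**Working it through.** **Step 1: which criteria can be met before stimulation?**

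| Criterion | Window in the text | Can it be met during baseline? |
|---|---|---|
| 1 | at stimulation current | No |
| 2 | during a stimulation session | No |
| 3 | whole study, which Patient Recruitment says includes baseline | Yes, on the words |
| 4 | none stated | Only by inference from silence |
| 5 | relative to baseline | No, since baseline is the reference |

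**Step 2: the two stopping rules side by side**

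| | Escape Criteria | Study Monitoring Committee |
|---|---|---|
| Threshold | 5 | more than five |
| What counts | any escape criterion | worsened seizures meeting the escape criteria |
| Scope | entire study | the site |
| Consequence | termination, automatic | suspension at the site; the Committee decides on termination |

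A patient not yet treated does not readily fit the second rule, so the answer to whether baseline events count depends on which section is followed.

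**Step 3: share of background events falling in baseline**

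The figure of 5 has no derivation in the protocol, so there is nothing to reproduce. For scale, assume rare events at a constant rate and full follow-up. The share is then baseline time / (baseline + treatment + follow-up). One month is taken as 4.345 weeks.

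- One-month baseline, 1 treatment week, 24 follow-up weeks: 4.345 / (4.345 + 1 + 24) = 4.345 / 29.345 = 0.148, about 15%.
- Patient Recruitment's two-month baseline and two-month follow-up, with 1 treatment week: 8.69 / (8.69 + 1 + 8.69) = 8.69 / 18.38 = 0.473, about 47%.
- The section on mitigating seizure risk mentions a three-month baseline. With 1 week (12/52 = 0.231 month) and 6 months after it: 3 / (3 + 6.231) = 0.325, about 33%.

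**Step 4: chance of a stop with no device effect (illustrative)**

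The protocol gives neither a sample size nor a background rate. Assume N = 12, 20 or 40 and 0.5%, 1% or 2% per patient-month for background events under criteria 3 and 4, with events under the other criteria ignored. The schedule is a 1-month baseline, then 1 week plus 6 months. The per-patient probability is p = 1 − exp(−rate × months), and the chance of a stop is P(X ≥ 5) for X ~ Binomial(N, p).

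Example at 1% per month: counting baseline, p = 1 − exp(−0.01 × 7.231) = 0.0698; counting only from first stimulation, p = 1 − exp(−0.01 × 6.231) = 0.0604. For N = 20 the tails are 0.0106 and 0.0058.

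| Rate per month | N = 12 | N = 20 | N = 40 |
|---|---|---|---|
| 0.5% | 0.0000 vs 0.0000 | 0.0006 vs 0.0003 | 0.0132 vs 0.0073 |
| 1% | 0.0009 vs 0.0004 | 0.0106 vs 0.0058 | 0.1438 vs 0.0916 |
| 2% | 0.0154 vs 0.0086 | 0.1214 vs 0.0762 | 0.6406 vs 0.5108 |

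(Baseline counted versus not counted.) The difference runs from 0 to 13 percentage points. The largest is 0.6406 − 0.5108 = 0.130, in a cell where the chance of a stop already exceeds one half without baseline events. Over the same grid, the largest difference is 0.2215 − 0.0292 = 0.193 for the two-month baseline and two-month follow-up, and 0.8274 − 0.5108 = 0.317 for the three-month baseline with 6 months of follow-up.

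**The case against.** The strongest case on the other side has five parts.

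- **Criterion 4.** A reader might infer that two criteria count baseline events. The text does not support that as a stated fact. Criterion 4 is silent on timing, and Exclusionary Criteria, item 3, bars a history or condition of status epilepticus, so an episode before treatment may be handled as ineligibility. This objection stands. No exclusion covers a first tonic-clonic seizure, so criterion 3 is unaffected.
- **The Committee's rule.** It is tied to worsened seizures and leaves termination to judgment, which suggests that untreated patients were not meant to count. That is a fair reading of intent, but it does not cure the automatic rule in Escape Criteria. It adds a conflict.
- **Purpose of the recruitment sentence.** It concerns keeping drug doses constant, not escape windows. True, but it states that the study includes the baseline, and the protocol does not define the study otherwise for criterion 3.
- **Small risk pool.** Only patients who have never had a tonic-clonic seizure can meet criterion 3, and entry requires at least two years of epilepsy. The background rate may be very low. This stands, and it limits the size of the problem.
- **Most background events come later.** Under the one-month schedule about 85% (1 − 0.148) would fall after treatment starts and would still count without attribution. Counting everything can be defended as cautious in an uncontrolled study. That is a separate and larger limitation. The events before stimulation are the part that certainly cannot be device effects.

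**Conclusion.** The point holds, as a minor one. On its words, the Escape Criteria section counts a first-in-life tonic-clonic seizure before any stimulation towards ending the whole study, and the Study Monitoring Committee section states an incompatible rule. For criterion 4 the reach into baseline is only an inference.

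The share of background events falling in baseline is about 15% with the one-month baseline and about 47% under Patient Recruitment's own schedule, both at an assumed constant rate. A reader might pair the two-month baseline with 24 follow-up weeks and obtain 8.69 / 33.69 = 26%, but no section describes that combination. A reader might also infer that a false stop is likely, or that a reported escape rate is inflated. Neither is supported. The probabilities above rest on assumed rates and sample sizes and are near zero over much of the grid, and the protocol defines no escape rate as an endpoint. The effect on the chance of a false stop is unknown and may be small.

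**What to change.** The sponsor should reconcile Patient Recruitment, Escape Criteria and Study Monitoring Committee so that the study-level count has:

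- one stated starting point, making explicit whether events before first stimulation count and whether a probe session is the first stimulation;
- one set of counted criteria, including the window for criterion 4 and its relation to exclusion 3;
- one threshold, one scope (site or whole study) and one decision maker.

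Events before stimulation should still be recorded and reported separately. The baseline length should be made the same throughout. Which rule to adopt is for the sponsor and its clinicians and is not proposed here.

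The cost is a clause in Escape Criteria and matching edits in the other sections. No extra data are needed and no safety information is lost.

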As mentioned above, estimations of safe and painless operation with conventional (large square sponges) tDCS (Bikson, Datta, & Elwassif, 2009) have suggested charge densities range from 343-960 C/m² (.0343-.0960 C/cm²). However, this calculation makes the common assumption in the tDCS literature that current is distributed evenly over the surface of the sponge. Instead, as would be consistent with classical physics model of the flow of current in a conductor, the current is distributed at the edge of the sponge, such that much higher current (and charge) densities have actually been delivered to the scalp at these perimeter locations in the conventional tDCS studies.

The same tendency for current to flow at the perimeter of the conductor is observed in simulations with the small (1 sq cm) electrodes of the GTEN 100 (Figure 8). However, the larger number of electrodes leads to greater perimeter distribution of the total current (Figure 8, right).

The first step to minimize the risk of pain is informing subjects that they can stop the procedure at any time just by letting us know they want to stop. This sensitivity to the patient's communications is an integral part of GTEN technician training. In addition, we tell each patient how, in case of emergency, they can take the chin strap and pull the Net off their head.

However, patients with epilepsy need an effective treatment, which may require brain current levels that are as close as possible to those induced by TMS. The present GTEN 100 protocol targets a current density at each electrode of 200 μ A/cm². We therefore minimize the risk of pain through iontophoretic (current induced) delivery of lidocaine that is mixed with the electrolyte. After a few minutes of iontophoretic application of lidocaine, our preliminary studies suggest 200 μ A/cm² is painless. If the subject detects any pain or discomfort, the current will be reduced so that the GTEN protocol (pulsed or sustained) is in fact painless.

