In the next series of experiments (now in preparation for publication), we tested the comfort level with higher current levels (200 μA for each 1 cm^2 electrode), using the typical tDCS protocol. Iontophoretic impedance conditioning was used to lower typical electrode-scalp impedances to 20 to 40K Ohms. There were large individual differences with comfort as well, but with the Geodesic Sensor Net 1 cm^2 electrodes and 7 to 10 with the primary cathodal or anodal current, most subjects reported minimal or no sensation at 50 μA , feelings of itching or minor pain at 100 μA , and noticeable itching and painful irritation at 200 μA . We then mixed lidocaine with the gel electrolyte, applied anodal current for iontophoretic delivery (see above for dose analysis) during the iontophoretic impedance conditioning, and then repeated the experiments at 200 μA . Subjects consistently reported this was a painless procedure. Only when we asked them to feel the scalp with their fingers did they notice the slight numbing of the scalp under the active (7 to 10 focal anodal or cathodal) electrodes.

We have now completed testing with normal volunteers with the Pulsed GTEN protocol. Initial tests (with the investigators) without lidocaine confirm that the pulsed stimulation is more painful than ramped and sustained tDCS, even at 100 μA . However, with the lidocaine iontophoresis, the 200 μA per electrode results in no noticeable sensation with the pulsed protocol. These pulsed experiments will be completed and submitted for publication, with the requirement that safety and comfort are both verified with normal volunteers prior to initiating clinical feasibility trials with the Pulsed GTEN protocol.

Therapeutic Mode of Action

In addition to insuring safety, we want to suppress seizures effectively. The literature on electrical neuromodulation in epilepsy suggests that tDCS typically has only a short term therapeutic effect in suppressing epileptiform discharges or EDs (Auvichayapat et al., 2013; Faria, Fregni, Sebastiao, Dias, & Leal, 2012). However, other evidence (Monte-Silva et al., 2013; Monte-Silva, Kuo, Liebetanz, Paulus, & Nitsche, 2010) suggests that repeated blocks of tDCS can induce lasting changes in cortical excitability (even though these studies were not with epilepsy).

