The primary endpoint is a temporary suppression of epileptic spikes. With assessments of spike rates at weeks 2, 4, 8, 16, and 24, the study will allow estimation of how temporary a suppression is achieved by the one-week treatment. The routine dEEG sessions typically collect dEEG for over an hour, and spike rates per hour will be the standard metric. To be successful, and to warrant progression to a randomized clinical trial, this clinical feasibility study must demonstrate successful targeting and suppression of the epileptogenic zone, as evidenced by temporary but statistically significant spike suppression in contrast to the pre-treatment baseline. All spike rates (baseline, treatment, and follow-up) will be counted as spikes per hour and classified in relation to waking or sleep stage (N1, N2, N3).

Secondary Endpoints and Study Success

The secondary endpoint is monthly suppression of seizures, assessed by the seizure diary each month for six months following treatment, in comparison to the mean seizure frequency for the one-month pre-treatment evaluation baseline. It is clearly advantageous if there is seizure as well as spike suppression as we plan the design of the pivotal trial.

Additional secondary endpoints will be (1) any improvement of cognitive function testing beyond the practice effect (estimated from norms and the improvement in the sham control group); (2) any improvement in quality of life ratings.

Study Monitoring Committee

The safety and comfort decisions for each patient are made by the epileptologist at each site. The safety, comfort, and efficacy of each treatment protocol across sites are reviewed by the Study Monitoring Committee. Vigilance will be maintained throughout the pivotal study to insure safety (no provoked seizures and no adverse effect to non target brain regions). Treatment will be discontinued for any patient that shows treatment-induced seizures, defined as seizures that are not the patient's typical seizures or that occur twice as frequently as the patient's typical seizures, as assessed during baseline. If there are more than five patients with worsening seizures (meeting escape criteria as stated above), the treatment will be suspended at that site. The Study Monitoring Committee (and the FDA when possible) will decide if the trial with that treatment should be terminated at all sites.

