- There is minimal risk of the treatment. The slow pulsed electrical neuromodulation has been applied in several studies of epilepsy with the TMS procedure, and there is no evidence that it causes seizures. Transcranial electrical stimulation (tDCS) has been applied in several experimental studies of patients with epilepsy, with no evidence that it causes seizures. Nonetheless, there is always a small risk of causing seizures, and medical procedures are in place both to monitor for seizures (with the EEG recording in each session) and to provide first aid if a seizure occurs.

- The primary feeling of the electrical current is a tingling sensation, and there is risk of minor itching and/or scalp pain. A small amount of lidocaine is mixed in the electrolyte to minimize the pain at the electrode site, and the procedures will be adjusted to assure that any discomfort is acceptable to the patient. Each patient should understand that they should speak up if there is any discomfort, that the technician is trained to carefully monitor their comfort level, and that they can quit the treatment at any time by simply saying they want to quit. If there is any emergency, the patient is shown how to simply pull the Geodesic Sensor Net off the head.

Changes to the Harborview Informed Consent Form

The Informed Consent Document (ICD) approved with the GTEN IDE was the EGI Consent Form (GTEN) 12/29/2014. This was rewritten to conform to the format of the University of Washington IRB and approved by the UW IRB. It was then modified to include the probe test (as described in the present protocol) and approved in November 2015. A minor error (stating the probe test was 10 min rather than 17 min) was corrected and the correction was approved March 9, 2016.

The EGI Parental Consent Form approved with the IDE is unchanged, but is not in use because the only active trial site (UW Harborview) is not enrolling adolescents.

Both the EGI IRB Consent form of December 29, 2014 (approved with the IDE) and the UW IRB Consent Form (proposed for this trial with the present Supplement) are attached.

With the exception of the probe test, there are only minor differences in these consent forms, involving the change of format to the UW IRB Consent Form format. Following is a section-by-section summary of the revision, emphasizing where the same information from the (IDE approved) EGI IRB Consent Form is included in the UW IRB Consent Form.

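### The study-wide limit of 5 escapes makes the site rule of more than five worsening-seizure patients unreachable, and no clause says which governs

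*Protocol*

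**What the plan says.** **Protocol, Escape Criteria.** Five criteria end the study for an individual patient. The first is "Unacceptable discomfort or pain at stimulation currents of 200" μA. The others are a tonic-clonic seizure in a stimulation session, a first-in-life tonic-clonic seizure, status epilepticus, and a doubling of seizure frequency from baseline. The section closes with the study-wide rule: "The entire study will terminate if 5 subjects meet escape criteria". No discretion is attached to it.

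**Protocol, Study Monitoring Committee.** "If there are more than five patients with worsening seizures (meeting escape criteria as stated above), the treatment will be suspended at that site". Then: "The Study Monitoring Committee (and the FDA when possible) will decide if the trial with that treatment should be terminated at all sites". The same section says that treatment is discontinued in a patient whose seizures are atypical or twice as frequent as at baseline.

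**Protocol, Monitoring of Risk.** For a two-fold seizure increase, treatment is suspended, and the epileptologist, patient and family then evaluate safety.

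**Protocol, Mitigating the Risk of Pain in Normal Operation.** "If the subject detects any pain or discomfort, the current will be reduced".

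**Protocol, Changes to the Harborview Informed Consent Form.** One site is running: "the only active trial site (UW Harborview) is not enrolling adolescents".

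**The concern.** The two rules differ in four respects: the count (5 against 6 or more), the events counted (any escape against worsening seizures only), the scope (whole study against one site) and the authority (automatic against committee decision). The site rule borrows the escape criteria by cross-reference, so the two count overlapping patients. A tiered scheme needs the site tier to fire before the study tier. Here the site tier has the higher count and the narrower event set.

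This is the study-level safety limit of an open-label, uncontrolled trial whose goals include safety. Someone working from the committee section alone could believe that no group-level action is due until the sixth worsening-seizure patient. Someone working from Escape Criteria would already have closed the trial.

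Two smaller gaps affect the count. The pain section lowers the current, and the Protocol does not say whether a patient who then continues has met criterion (1). A two-fold seizure increase leads to study termination for the patient in one section, discontinuation of treatment in another, and suspension with evaluation in a third. The third does not say whether the patient counts as an escape.

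**Working it through.** There is no planned sample size, power figure or expected escape rate to reproduce, and none is needed. The check is a count.

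**Inputs**
- Study-wide limit: 5 subjects meeting any escape criterion (Escape Criteria).
- Site threshold: more than five, so at least 6, worsening-seizure patients who meet the escape criteria (Study Monitoring Committee).
- Sites: three planned (Clinical Feasibility Trial Design), one active (Changes to the Harborview Informed Consent Form).

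**Step 1: who is counted.** Let W be the number of worsening-seizure patients who meet escape criteria and K the number of other escapes. The study-wide rule counts W + K. The site rule counts W, or only the part of W at one site. Since W ≤ W + K, the site rule's patients are a subset.

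**Step 2: can the site rule be reached?** The study runs only while W + K ≤ 4, so W ≤ 4, and the site rule needs W ≥ 6. An enumeration confirms this. With three sites and two escape types there are six counts; the number of ways they can total 4 or fewer is C(10, 6) = 210. None of the 210 meets the site rule, whether more than five is read per site or over all sites. If several escapes were recorded at the same moment and the total jumped from 4 or fewer to 6 or more, the study-wide rule would be met as well.

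**Step 3: how far apart are the rules if the site rule is relied on?** Take one active site. The study-wide rule stops at W = 5 − K; the site rule suspends at W = 6. The gap is 6 − (5 − K) = 1 + K.

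| Other escapes, K | Study-wide rule stops at W | Site rule suspends at W | Gap |
|---|---|---|---|
| 0 | 5 | 6 | 1 |
| 1 | 4 | 6 | 2 |
| 2 | 3 | 6 | 3 |
| 3 | 2 | 6 | 4 |
| 4 | 1 | 6 | 5 |
| 5 | 0 | 6 | 6 |

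K includes pain exits but is not limited to them. A tonic-clonic seizure in a session is an escape under criterion (2), yet it may be the patient's habitual seizure and so need not be worsening. Mitigating the Risk of Seizures in Normal Operation describes in-session seizures under slow rTMS as typical of the patients who had them. If d is the number of pain exits alone, 1 + d is therefore a minimum.

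**Step 4: the two-fold increase.** Suspension (Monitoring of Risk) followed by discontinuation (Study Monitoring Committee) and study exit (Escape Criteria) can be read as one sequence. The Protocol does not set it out as one, and does not say at which step the patient enters the count of 5.

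**The case against.** The strongest reply is that the study-wide rule is unconditional and already the stricter one. A site that stops at five breaches nothing in the committee section, which is silent about the fifth escape. On this view the site rule is merely redundant. It also looks like carried-over text: its paragraph speaks of a pivotal study, the endpoint text nearby mentions a sham group in an uncontrolled trial, and Power Analysis and Missing Data Analysis still describes two treatment protocols although the Overview drops one. Much of this stands. But the site rule is current text, sits in this trial's design and refers back to this trial's escape criteria. If it is a leftover, the remedy is still to remove it.

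The gap may also be small in practice. In volunteers given lidocaine at 200 μA, "Subjects consistently reported this was a painless procedure", so pain exits may be few. That stands for K near 0, though these were not patients, and the gap is then still one.

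Patients are also protected one by one: "The safety and comfort decisions for each patient are made by the epileptologist at each site". That stands, and it bears on severity.

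Four stronger readings are tempting but unsupported:
- **That the Protocol directs the trial to continue at the fifth escape.** The committee section never says so.
- **That it is open whether pain exits count.** Criterion (1) is an escape criterion, so on the plain text they do. Only the patient who continues at reduced current is unclear.
- **That the gap is exactly one plus the number of pain exits.** Step 3 shows why that is a minimum.
- **That Monitoring of Risk permits treatment to resume after a two-fold increase.** It does not mention resumption.

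**Conclusion.** The point holds as a defect in how the group-level stopping rule is written. If the limit of 5 is followed, the site suspension and the committee decision after it are unreachable. If the site rule is relied on, treatment could pass that limit by at least one patient, and by one more for each escape that is not a worsening seizure. The size rests only on the two stated counts and the one active site; no sample size or event rate is assumed. The Protocol gives no expected number of pain exits or other non-worsening escapes, so the likely gap within the range 1 to 6 cannot be stated.

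A reader might infer that the trial lacks a usable safety limit or that patients are left unprotected. Neither follows: the stricter automatic rule is already there, and individual safety decisions stay with the site epileptologist. No endpoint or analysis depends on the conflict. It is a should-fix wording correction to a safety rule.

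**What to change.** 1. **One governing rule.** State that the study-wide limit of 5 in Escape Criteria governs. In Study Monitoring Committee, delete the threshold of more than five, or replace it with a site trigger below 5 that prompts committee review. The sponsor, the committee and FDA should choose the value.
2. **Pain.** State whether a patient who continues at reduced current after pain counts as meeting criterion (1).
3. **Two-fold seizure increase.** Align Monitoring of Risk with the other two sections: treatment is suspended at once and the patient counts as an escape.

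Two additions should be avoided. Measuring the two-fold increase over a full month, as the seizure endpoint does, could not stop a treatment course of five days in one week. Counting an escape only once it is confirmed would delay the count towards 5. A rule on follow-up after escape is not needed to resolve this conflict.

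The cost is wording in three sections, with a sentence on reduced current in Escape Criteria. The amended text may need FDA and IRB approval: the document is itself an IDE supplement, and it reports IRB approval of the safety procedures in Eugene and Seattle. No patients, visits or analyses are added.
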